### *Immunogenicity Evaluation*

[figure not shown]
Assessment of immunogenicity is a secondary objective in this study. Due to the prior vaccinations received by those to be enrolled into the study, baseline immunity (titer of type-specific neutralizing antibody) to poliovirus types 1 and 3 is expected to be high, with the level boosted by study vaccination. While it is expected that the presence of an immune response can be observed by an increase in neutralizing antibody titer following vaccination, and because the post-vaccination immunity is anticipated to exceed the assay upper limit of quantification (ULOQ) for some participants, definitive comparisons of study vaccination groups to the relevant control (nOPV vs type-specific control, within cohort according to prior vaccination [exclusively IPV vs OPV-containing]) will not be possible within this phase 1 study. Evaluation of immunogenicity, therefore, will be primarily descriptive in nature; comparisons to the relevant control will be made, but the sample size is not based on achieving a specific level of statistical power for these comparisons. Comparative evaluation for immunogenicity will focus on the cohorts previously receiving OPV vaccinations but will also be conducted among exclusively IPV-vaccinated participants.

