Prior studies of type 2 in OPV-vaccinated adult populations indicate baseline immunity within the quantifiable range, with mean  $\log_2$  neutralizing antibody (NAb) titers ranging from 7.8 to 8.8 (unpublished data), and with the majority of participants achieving NAb titer >ULOQ 28 days following a single dose of a Sabin-2 vaccine as well as investigational type 2 vaccines. Using a regression model permitting censoring at assay lower limit of quantification (LLOQ) and ULOQ, the standard deviation (SD) of post-vaccination NAb titers is estimated to be in the range of 3 – 3.5 on the  $\log_2$  scale, which is consistent with other published data for type 1 (prior to a boost vaccination in adulthood) [11]. In the study involving type 2, the post-vaccination GMT ratio (candidate/control) and its corresponding CI were able to be estimated; similar methods will be employed here (see below). With respect to binary immune response endpoints (seroconversion, other seroresponse rates), data from the type 2 study indicate seroconversion rates ranging from approximately 30% to 75%, depending on the vaccine and potency level administered. Rates of a minimum 2-fold response ranged from approximately 50% to 75%, with rates of any fold-rise ranging from approximately 60% to 85%.

Using these values, simulation studies were conducted to evaluate the precision of estimates of the GMT, GMT ratio, response rates, and differences in response rates, assuming that 48 and 24 of the 50 and 25 or 28 and 14 of the 30 and 15 prior OPV participants randomized to receive nOPV or mOPV, respectively, provide samples for analysis. The figure below displays the average half-width of the two-sided 95% confidence intervals for the four evaluations across the range of relevant inputs ( $\log_2$  NAb SD for GMts, true rate for the various response rates). The level of precision expected to be available, described within the figures, is considered adequate to determine if there is sufficient evidence of an immune response to warrant progressing into populations where the immune response may be more thoroughly described and compared.

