##### **11.5.6.1 Descriptive Analyses**

At each time point where NAb titers are obtained:

- Median of  $\log_2$  antibody titers will be computed along with 95% CIs
- GMT with accompanying 95% CIs will be computed. GMTs will be estimated with likelihood-based methods (SAS PROC LIFEREG) to accommodate censoring at assay ULOQ and LLOQ.
- The geometric mean fold rise (GMFR) will be computed for each post-baseline time point as the reverse-transformed difference between the post-baseline  $\log_2$  value and the baseline  $\log_2$  value and accompanied by two-sided paired-sample 95% CIs computed using asymptotic methods on the  $\log_2$  scale, then reverse-transformed. A subgroup analysis of GMFR will consider only those participants with values between the LLOQ and ULOQ (exclusive of the endpoints) for the numerator and denominator samples. For post-dose-2 GMFR, this will be computed from baseline, and from the pre-dose-2 titer. Among these participants, a plot of the  $\log_2$  fold rise vs the baseline  $\log_2$  antibody titer will be generated.
- Type-specific seroconversion rates with 95% exact CIs will be tabulated for post-vaccination time points. Seroconversion rate will be computed among those participants with seroconversion possible to observe (within 4-fold of the assay ULOQ). For post-dose-2 seroconversion, seroconversion rates will be computed both from baseline and from the pre-dose-2 titer

- In addition, the rate of any fold-rise (titer increased from baseline) and a minimum 2-fold rise in titer and accompanying CIs will be computed in the same manner
- Type-specific seroprotection rates with 95% exact CIs will be tabulated
- Plots of the reverse cumulative distribution of antibody titers will be generated

Additional figures will display immunity and changes in immunity over time, by type. Additional subgroup computations will be specified and conducted, per the SAP.

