#### **11.5.6.2 Comparative Analyses**

No specific immunogenicity hypothesis is to be tested. Descriptive comparative evaluation will be conducted with multiple endpoints; such evaluations will be conducted for the nOPV-vaccinated groups compared to the mOPV-vaccinated control groups within type, and within background vaccination cohort (within groups defined by exclusive IPV prior vaccination, and separately among those previously receiving OPV). Separately for each pairwise comparison, the NAb GMT ratio (nOPV/mOPV) will be estimated via a linear model of the  $\log_2$  NAb titer as a function of group with a fixed parameter for site and a covariate for the  $\log_2$  NAb titer level. This will be conducted using SAS PROC LIFEREG to account for censoring of the dependent variable assuming a Normal error distribution on the  $\log_2$  scale; baseline values achieving ULOQ or LLOQ will be replaced with ULOQ or LLOQ, as appropriate, for the covariate. The log-scale difference and its corresponding confidence interval, estimated with SAS LSMEANS, will be reverse-transformed to obtain the estimated GMT ratio and corresponding 95% confidence interval. Among the subset of participants where baseline and post-baseline NAb titers are below the assay ULOQ, the fold-rise in titer will be computed, and these fold-rises will be compared between nOPV vs mOPV groups within background vaccination cohort and type using standard *t*-distribution methodology.

Similar comparisons will be made for seroprotection rates, seroconversion rates, and other response rates (any fold-rise, 2-fold rise). For these binary variables, two-sided 95% Miettinen and Nurminen confidence intervals for the rate difference (nOPV minus mOPV) will be computed, and these will be supplemented with a two-sided Fisher exact test p-value.

Imbalance in baseline immunity between sites will be evaluated via the Kruskal-Wallis test for Nab titers. Wherever the global test is significant at two-sided level  $\alpha = 0.10$ , pairwise comparisons will be drawn from the Wilcoxon test.

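### The between-arm fold-rise comparison keeps only participants whose post-vaccination titre stays below the ULOQ, so it selects on the outcome and pulls a true nOPV–mOPV difference toward zero

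*Protocol*

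**What the plan says.** Protocol 11.5.6.2 (Comparative Analyses) first plans the nOPV/mOPV GMT ratio. It is a linear model of log2 titre with site and a titre covariate, fitted with PROC LIFEREG so that titres at the assay limits count as censored. The section then adds a second comparison: "Among the subset of participants where baseline and post-baseline NAb titers are below the assay ULOQ, the fold-rise in titer will be computed". A t-based method then sets the two arms against each other on this measure, separately by type and by prior-vaccination cohort. The section does not call this second comparison supplementary and does not mention a bias.

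Section 11.5.6.1 (Descriptive Analyses) uses PROC LIFEREG for the GMT. The all-participant GMFR gets only a paired asymptotic CI, and the section does not say how titres beyond the ULOQ enter. It also plans a within-range version: "A subgroup analysis of GMFR will consider only those participants with values between the LLOQ and ULOQ (exclusive of the endpoints").

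On how often the ULOQ is reached, section 11.3 (Immunogenicity Evaluation) describes earlier type 2 studies in OPV-vaccinated adults, "with the majority of participants achieving NAb titer >ULOQ 28 days following a single dose". For this trial it says less: "because the post-vaccination immunity is anticipated to exceed the assay upper limit of quantification (ULOQ) for some participants".

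**The concern.** A restriction on baseline titre is harmless to a randomised comparison, because baseline is fixed before allocation. A restriction on the post-vaccination titre is not. A participant who responds past the ULOQ leaves the analysis and one who responds weakly stays. If one vaccine is more immunogenic, it loses more of its good responders, so the retained groups look more alike than the randomised groups are. A t comparison of what remains estimates neither the difference in all participants nor the difference in any group defined before vaccination.

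The practical risk is two between-arm results on the same titres that disagree without explanation: a censored GMT ratio showing a difference, and a fold-rise comparison showing much less of it. Section 11.3 reads its intervals against 2-fold and 4-fold bounds, so a halving on the log2 scale would change how the fold-rise result is read.

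**Working it through.** **Inputs from protocol 11.3.** Post-vaccination SD: "the standard deviation (SD) of post-vaccination NAb titers is estimated to be in the range of 3 – 3.5" on the log2 scale. Baseline mean log2 "titers ranging from 7.8 to 8.8 (unpublished data"). Evaluable participants 48:24 or 28:14.

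**Step 1: the plan's own figures.** The half-width of the 95% CI for a difference in mean log2 titre is 1.96 × SD × √(1/n1 + 1/n2).
- SD 3, 48:24: 1.96 × 3 × 0.250 = 1.47 (stated 1.48)
- SD 3, 28:14: 1.96 × 3 × 0.327 = 1.92 (stated 1.92)
- SD 2: 0.98 and 1.28 (stated 0.97 and 1.25)

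All agree within 3%. These figures use every evaluable participant. The subset comparison does not.

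**Step 2: a case that can be done by hand.** Assume baseline and post titres are uncorrelated, SD is 3, and half of controls exceed the ULOQ, so the control mean equals the ULOQ (call it c). The baseline restriction then cancels between arms, and the mean post titre of those kept is μ − SD × φ(a)/Φ(a), with a = (c − μ)/SD.
- Control, μ = c: c − 3 × 0.3989/0.5000 = c − 2.394
- nOPV 1 log2 lower (2-fold deficit), a = 1/3: c − 1 − 3 × 0.3774/0.6306 = c − 2.795. Difference −0.40 instead of −1, a shrinkage of 60%.
- nOPV 2 log2 lower (4-fold deficit), a = 2/3: c − 2 − 3 × 0.3194/0.7475 = c − 3.282. Difference −0.89 instead of −2, a shrinkage of 56%.

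In the 4-fold case the post-baseline condition alone keeps 75% of nOPV but 50% of mOPV.

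**Step 3: with correlation.** Bivariate normal log2 titres were simulated, 1,000,000 per scenario, keeping only baseline and post values below the ULOQ. Assumed, because the protocol does not give them: correlation 0 to 0.7, baseline SD 2 or 3, baseline mean 1.2 or 2.2 log2 below the ULOQ, and the share of controls above the ULOQ. Post SD was 3 or 3.5; true shifts were ±1 and ±2 log2. Shrinkage of the true difference (%, minimum–maximum):

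| Correlation | 20% above ULOQ | 30% | 40% | 50% | 60% | 70% |
|---|---|---|---|---|---|---|
| 0 | 32–51 | 41–59 | 49–65 | 56–70 | 62–74 | 67–79 |
| 0.3 | 23–42 | 30–49 | 37–55 | 43–60 | 48–64 | 53–68 |
| 0.5 | 16–36 | 23–43 | 29–49 | 34–53 | 38–56 | 41–59 |
| 0.7 | 10–30 | 15–36 | 20–41 | 24–44 | 26–47 | 27–49 |

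With at least half of controls above the ULOQ the range is 24–79%, median 52%. With 20–40% above it is 16–49% at correlation 0.5, and 10–65% over the whole grid. The sign never reversed.

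**Step 4: the censored model on the same data.** True difference 1.0 log2, SD 3, 50–60% of controls above the ULOQ, correlation 0.3–0.5. With 20,000 per arm the subset gives 0.36–0.58 and censored regression on all participants gives 0.96–1.04. At 48:24 the subset averages 0.38–0.55 on about 12–16 nOPV and 9–11 mOPV participants; censored regression averages 0.95–0.97. At 28:14 (correlation 0.5, 60% above) the subset keeps about 8 and 5 participants. Two runs there gave 0.49 and 0.45 for the subset against 0.80 and 0.93 for the censored model. Some small-sample error is therefore possible in the censored model, but it is far smaller than the subset's bias.

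**The case against.** The strongest reply is that little rests on this comparison, and most of that reply stands. Section 2.3.2 lists median titre, GMT, the baseline-adjusted GMT ratio and response frequencies; mean fold-rise between arms is not among them. Section 11.5.6.2 tests no immunogenicity hypothesis, and section 11.3 says that definitive comparisons with control will not be possible and are planned for later phases. The listed comparative endpoint already handles the censoring. Moreover, once baseline is a covariate, modelling the post titre or the fold-rise gives the same group coefficient, so a corrected fold-rise comparison comes close to repeating the GMT ratio.

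Four stronger readings are tempting and are not supported:
- A reader might infer that the protocol expects most participants here to exceed the ULOQ. The majority in section 11.3 belongs to type 2 studies in OPV-vaccinated adults. For this trial the text says some participants, and it gives no figure for types 1 and 3 or for the IPV-only cohorts.
- A reader might infer that a true nOPV deficit would go unseen. It would show in the censored GMT ratio.
- A reader might take one shrinkage figure as fact. Every figure depends on a ULOQ and a correlation that the protocol does not state.
- A reader might infer that the GMFR is understated. That follows only if post-dose titres beyond the ULOQ are set to the ULOQ, and section 11.5.6.1 does not say so. Such an understatement would also make an immune response harder to show, so it would be conservative for the decision to progress.

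What the reply does not remove is that the protocol specifies an outcome-selected comparison between arms, without a supplementary label or a warning.

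**Conclusion.** The point holds as a limited one. The fold-rise comparison in section 11.5.6.2 selects on the post-randomisation outcome and is biased toward no difference. Given bivariate normal log2 titres and the protocol's SDs, shrinkage is roughly 25–80% if at least half of controls exceed the ULOQ, as the type 2 precedent suggests. It is about 15–50% at correlation 0.5 if only 20–40% do. The direction is certain under this model; the size is not. The effect is confined to one descriptive comparison that is not a listed endpoint, and the baseline-adjusted GMT ratio is unaffected. It should be corrected because the text states a biased method where an adequate one is already planned alongside it.

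**What to change.** In section 11.5.6.2, and in the SAP where it carries the text over:
- Delete the condition that the post-baseline titre be below the ULOQ. Estimate the fold-rise difference in all participants with baseline below the ULOQ, using the planned PROC LIFEREG model with post-dose log2 titre right-censored at the ULOQ. Keep baseline titre as a covariate: on the fold-rise scale the censoring limit is the ULOQ minus baseline, so the model must condition on baseline. State that the result is expected to lie close to the GMT ratio.
- Keep the within-range subset only as a description or plot by arm, without a between-arm test or interval, and say that it understates differences.

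In section 11.5.6.1, obtain the all-participant GMFR by the censored likelihood already planned for the GMT, with an interval that respects the pairing of baseline and post titres, and state how values beyond the ULOQ enter.

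The cost is wording and a small amount of programming. No new data, visits or participants are needed.

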#### **11.5.7 Viral Shedding Analysis**

Only participants receiving a dose will be evaluated for viral shedding in the corresponding post-dose period. The SAP will provide detail about participants selected into each analysis.

##### **11.5.7.1 Descriptive Analyses**

For each group and time point, viral shedding positivity (PCR) and infectivity ( $\log_{10}$  CCID50 per gram) will be summarized. Additional summary of infectivity will be conducted only among those PCR-positive for (only) the vaccine virus. Positivity will be accompanied by two-sided exact 95% confidence intervals for the proportion, and infectivity will be summarized with the median and bootstrap-based 95% CI. All samples will be evaluated for the appropriate virus type (1 or 3). Participants PCR-positive for type-specific viral shedding of only the appropriate virus but with  $\log_{10}$  CCID50 per gram equal to LLOQ will contribute a value equal to the LLOQ; participants PCR-negative for viral shedding of the appropriate virus will contribute zero. A summary will also be produced for each post-dose period of the proportion of

participants contributing any PCR-positive sample, any culture-positive sample ( $\geq 2.75 \log_{10} \text{CCID}_{50}$  per gram), and those with  $\log_{10} \text{CCID}_{50}$  per gram  $\geq 4.0$ )

The Shedding Index Endpoint (SIE) will be computed as the mean of the  $\log_{10} \text{CCID}_{50}$  per gram from nominal collection days 7, 14, 21, and 28 post-dose (e.g., study days 8, 15, 22, and 29 following the first dose). An additional summary table will describe the samples considered to be within-window for computation of the Shedding Index Endpoint. Permissible stool sample windows will mirror the visit windows defined in this protocol. The SIE will be computed for each participant contributing samples at each time point, and will be summarized by group, including the median and its bootstrap-based 95% confidence intervals. The SAP will define the AUC computations for each post-dose period, which will be summarized similarly.

Time to cessation of shedding is defined as the time (days) between vaccination and last PCR-positive stool prior to 2 consecutive PCR-negative stools (with a minimum 24-hour interval between the 2 negative stools). The time to cessation of shedding will be assessed with interval-censored methodology to describe and compare the duration of shedding. Similarly, supplementary definitions of shedding negativity (culture-negative, defined as the last culture-positive value, and “transmission-negative”, defined as the last value with  $\geq 4.0 \log_{10} \text{CCID}_{50}$  per gram) will be described in the SAP, and evaluated with methods accommodating censored data. The methods for considering participants censored will be further defined in the SAP.

Descriptive analysis and plots of the reverse cumulative distribution of the daily infectivity assay results, the SIE, and the AUC will be generated. Additional figures will display the shedding of virus over time.

Additional subgroup analyses may be specified in the SAP.

#### **11.5.7.2 Comparative Analyses**

Comparisons of viral shedding data will be made within type and within background vaccination group (exclusively IPV and OPV-containing). Rate of shedders (PCR, culture-positive, etc.) will be compared at each time point using summary statistics, as well as 95% score-based confidence intervals for the difference in proportions at each time point. The  $\log_{10} \text{CCID}_{50}$  per gram will be compared between groups with a Wilcoxon test for the difference between groups, accompanied by the difference in medians and accompanying bootstrap-based 95% confidence interval, both overall and among only those PCR-positive for (only) the appropriate virus. The same methods will be used for the SIE and AUC.

Tests between nOPV and mOPV for time-to-shedding cessation endpoints will be conducted with two-sided log-rank tests using a Type I error rate of 5%.

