### *Intestinal Immunity, Genetic Stability*

In recognition that previously OPV-vaccinated participants are unlikely to shed vaccine virus in substantial quantities, the 30-40 participants for each type with exclusive prior IPV vaccination to be randomized 1:1 to nOPV or mOPV are included primarily to provide a preliminary indication of intestinal take (shedding of virus, indicating replicating infection), as well as to provide samples for potential genetic stability analysis of shed virus, including NGS and evaluation in a mouse neurovirulence assay. The relevant

neurovirulence assay for comparison to Sabin-strain vaccines is yet to be developed, but it is anticipated that a null hypothesis of no difference, vs. an alternative hypothesis of superiority of nOPV to mOPV will be evaluated from this model; a defined level of statistical power is not a requirement for this preliminary evaluation. It is currently unknown what levels of paralysis may be seen in transgenic mice in such an assay as assay development is ongoing but based on preclinical data indicating no paralysis associated with passaged candidate vaccine virus, and the known reversion to neurovirulence resulting in frequent paralysis of mice inoculated with reverted Sabin-strain vaccines, sufficient discriminatory capability is expected to be provided by 15-20 participants per vaccine.

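### For shedding quantity, the overall difference in medians is exactly 0 when fewer than half shed in both arms, and its bootstrap interval becomes (0, 0) when observed shedding is about 20–34% or less

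*Protocol*

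**What the plan says.** Protocol 11.5.7.2 (Comparative Analyses, viral shedding) sets a Wilcoxon test for shedding quantity in each nOPV–mOPV pair. The test result is to be reported "accompanied by the difference in medians and accompanying bootstrap-based 95% confidence interval". This is done overall and again among participants PCR-positive for the vaccine virus only. On the two summary measures the section adds: "The same methods will be used for the SIE and AUC".

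Section 11.5.7.1 fixes the scoring: "participants PCR-negative for viral shedding of the appropriate virus will contribute zero". The SIE is the mean of the log10 values "from nominal collection days 7, 14, 21, and 28 post-dose". The AUC computation is left to the SAP.

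Section 11.3 (Intestinal Immunity, Genetic Stability) expects that "previously OPV-vaccinated participants are unlikely to shed vaccine virus in substantial quantities". The IPV cohorts, at 15–20 per arm, are introduced there as "the 30-40 participants for each type with exclusive prior IPV vaccination to be randomized 1:1 to nOPV or mOPV". In the OPV-history cohorts the arms are 30–50 on nOPV and 15–25 on mOPV (Section 3, schema).

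**The concern.** Scoring non-shedders as zero puts a point mass at zero. A median ignores everything above that mass until at least half the arm sheds, so at low shedding the difference in medians does not respond to how many shed or how much. The Wilcoxon test does respond. The two figures placed side by side can therefore disagree: a test that finds a difference, and an estimate with an interval that says zero.

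Extent of shedding by SIE and AUC against the homotypic Sabin vaccine is a secondary objective in IPV-only participants (2.2.2) and an exploratory one in OPV-history participants (2.2.3). For both, the difference in medians is the only effect estimate with an interval on the log10 scale that uses the whole randomized comparison. A row reading 0 (0, 0) looks like precise equality when it only reflects that most participants in both arms had no virus.

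**Working it through.** The protocol states no power or precision for the shedding comparisons, so there is no figure of its own to reproduce.

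**Inputs from the protocol.** Non-shedders score 0 (11.5.7.1). Arm sizes are 15–20 (IPV) and 30–50 against 15–25 (OPV) (Section 3). Tests and intervals are two-sided at 5% (11.5.1).

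**Assumed inputs.** Shedding rates are not given. Shedder titres are taken as normal with mean 4.5 and SD 1 log10, floored at 2.75, the culture-positive cut-off in 11.5.7.1. The thresholds in step 1 do not depend on the titres.

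**Step 1: thresholds.** With k shedders of n, the sample median is 0 while k is below (n+1)/2 for odd n, or below n/2 for even n. A bootstrap resample has a non-zero median with probability P(Bin(n, k/n) ≥ (n+1)/2) for odd n, or ≥ n/2 for even n. That arm leaves its side of the percentile interval at 0 while this probability is below 0.025.

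| n | Median 0 up to | Interval end 0 up to | Probability at that k | At k+1 |
|---|---|---|---|---|
| 15 | 7 (47%) | 3 (20%) | 0.004 | 0.0255 |
| 20 | 9 (45%) | 5 (25%) | 0.014 | 0.048 |
| 25 | 12 (48%) | 7 (28%) | 0.010 | 0.030 |
| 30 | 14 (47%) | 9 (30%) | 0.017 | 0.043 |
| 50 | 24 (48%) | 17 (34%) | 0.014 | 0.0295 |

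Both arms must meet the limit for the interval to be (0, 0). Between the two limits the interval is usually wide with one end at 0: 0/20 against 9/20 gives 0 (about −4, 0).

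**Step 2: examples (nOPV first).**

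- 1/50 against 7/25: median difference 0 (0, 0), Wilcoxon p < 0.001, rate difference −26% (−46%, −11%).
- 0/20 against 5/20: median difference 0 (0, 0), Wilcoxon p = 0.020, rate difference −25% (−47%, −7%).

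**Step 3: frequency under assumed rates.** The chance of (0, 0) is about P(k1 ≤ limit) × P(k2 ≤ limit).

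- 50:25, 2% against 20%: P(Bin(50, 0.02) ≤ 17) × P(Bin(25, 0.20) ≤ 7) = 1.00 × 0.89 = 0.89. Simulation gave 90%, and 68% of trials paired (0, 0) with Wilcoxon p < 0.05.
- 20:20, 5% against 25%: 1.00 × P(Bin(20, 0.25) ≤ 5) = 0.62. Simulation gave 60%, and 12% paired with a significant test.
- 20:20, 5% against 45%: 1.00 × P(Bin(20, 0.45) ≤ 5) = 0.055. Simulation gave 6%.

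**Step 4: SIE.** It is 0 only if all four days are negative. If days were independent, P(SIE > 0) = 1 − (1 − p)^4. This is 0.34 at p = 0.10 and 0.59 at p = 0.20, so at 20% per day the median would not be 0. Strong within-person correlation would bring the share closer to the daily rate.

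**Step 5: alternatives on the same data.** For 1/50 against 7/25, the probability that an mOPV value exceeds an nOPV value, ties counted half, has three parts. mOPV shedder against nOPV zero is 7/25 × 49/50 = 0.274. Half of the zero–zero pairs is 0.5 × 18/25 × 49/50 = 0.353. About half of the shedder–shedder pairs is 0.5 × 7/25 × 1/50 = 0.003. The sum is 0.63, with bootstrap interval (0.54, 0.72). For 0/20 against 5/20 it is 5/20 + 0.5 × 15/20 = 0.625 (0.525, 0.725). The Hodges-Lehmann shift is 0 in both cases.

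**The case against.** The strongest reply is that the median difference does not stand alone. Section 11.5.7.2 also gives score intervals for differences in shedding rates at each time point, including culture-positive rates, which carry some information on amount. Section 11.5.7.1 tabulates the proportions with any culture-positive sample and with at least 4.0 log10, and plans reverse cumulative distribution plots of daily results, SIE and AUC. A reader might infer that the plan hides a real difference in shedding. It does not, because these outputs would show it. That part of the reply stands.

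A reader might also infer that the interval collapses whenever fewer than half shed. One half is the limit for the estimate only. The interval reaches (0, 0) at clearly lower shedding, and in both arms. At 20:20 with 5% against 45% it does so in only about 6% of trials.

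Nor do the documents support saying that SIE and AUC fail equally. The SIE needs four negative samples to be zero, and the AUC cannot be judged before the SAP defines it.

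Finally, the stakes are modest. The stated expectation of little shedding concerns the cohorts where extent is exploratory, no decision rule uses this interval, and 11.3 defers definitive shedding evaluation to later phases.

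What remains is that rates dichotomise amount, the Wilcoxon p value is not an effect size, the plots carry no interval, and the PCR-positive comparison conditions on a post-randomization outcome.

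**Conclusion.** The point holds as a narrow one. The overall difference in medians is exactly 0 when fewer than half of both arms have a non-zero value. Its interval is exactly (0, 0) when observed shedding is at or below 3/15, 5/20, 7/25, 9/30 or 17/50 in both arms. In those situations the only full-population effect estimate on the quantity scale is uninformative and can sit beside a significant Wilcoxon test.

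The thresholds follow from the scoring rule and a percentile bootstrap. The frequencies rest on assumed rates, since the protocol states none. The problem is most likely in the OPV-history cohorts, possible at late stools in the IPV cohorts, less frequent for the SIE, and undetermined for the AUC. It is a reporting weakness worth a cheap correction; it does not undermine the shedding objectives.

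**What to change.** In 11.5.7.2, for the overall comparisons of log10 CCID50 per gram, SIE and AUC, report the Mann-Whitney probability (nOPV lower than mOPV, ties counted half) with a 95% CI as the effect measure accompanying the Wilcoxon test. It is the quantity that test addresses. Keep the difference in medians for the PCR-positive subset, and overall as a secondary descriptive figure where at least half of an arm sheds.

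The Hodges-Lehmann shift should not be the replacement, since it is also 0 in the examples. Nor should the bootstrap mean difference be relied on: in simulation with 10% shedding its false-positive rate was 8–10%.

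The cost is a wording change and one table column, with no new data. The downside is a less familiar measure that is not on the log10 scale and is pulled towards 0.5 by ties. If nobody sheds in either arm, its bootstrap interval would also have zero width, and only the rate difference with its score interval is informative.
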